
As mentioned above, risks of the *Exersides™* restraint are very low. Nevertheless, we have taken the following steps and safeguards in the study protocol to minimize such risks and protect against them:

1. Data will be kept secure and confidential
2. Treating physicians will be allowed to exclude patients from the study

Additionally, we will submit a plan for monitoring of adverse events to the study's Data and Safety Monitoring Board (DSMB). Serious adverse events that might bear any relationship to the intervention will be reported to the local IRB as well as the University of Vermont Human Subjects Committee (parent site) and the DSMB, which may elect to restrict or cease enrollment. See Data and Safety Monitoring Plan. Furthermore, a medical/site monitoring plan is in place whereby a Study Monitor will visit each site at least twice during the study to assess protocol compliance and conduct source verification. During the site visit, case report forms will be reviewed for quality control.

Finally, data presentations will include only group data and will be presented in a way that ensures individual participants cannot be identified. If respondents may be identified by a specific subgroup analysis due to the low numbers of these types of respondents (e.g., patients aged >90), these subgroup data will not be presented in isolation in any format. There is a small risk of breach of confidentiality with the addition of video recording of subjects while in the novel and wrist restraints. We will take steps to minimize this risk by angling the camera to reduce capture of medical personnel and family members who are also in the room. A sign will

be posted on the door to alert anyone entering the room that a camera is in use. The recordings will be removed from the video camera / storage card as soon as possible, and downloaded to a secure server. We will encrypt the recordings for storage during the study, and require two-factor authentication for access. The footage will be reviewed by authorized study staff in a timely manner and the extracted data will be identified only by the subject's Study ID. After the data is extracted, the video recordings will be destroyed.

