3. The DSMB will also approve the DSMB Charter and review any conflicts of interest that have been disclosed.

4. Recommendations: Voting in closed session, the DSMB can recommend that the trial continue with no modifications, continue with modifications, or stop for safety concerns. The chair or designate will summarize major points of discussion, decisions, actions, and reasons, and additional information needed for future meetings. The report will be provided to study's Principal Investigators for submission to the study sites' IRBs.

ii. Interim meetings:

Meetings will occur after 1/2 (n=27) of the total participant sample (n=54) have completed all study procedures. Ad hoc meetings can be requested by the PI or DSMB if an unanticipated safety signal is identified. The DSMB will evaluate all of the items outlined above in the safety review (3b(ii)). Recommendations from the DSMB will also be summarized as outlined above (3b(iii)). During this interim meeting, the DSMB will review data for recruitment, randomization, subject retention, protocol adherence, intervention effects, gender and minority inclusion, and participant safety. The DSMB will receive cumulative data, including safety events that are reported to the IRB (as described below) and major clinical outcome variables prepared by the trial biostatistician. They may perform its own statistical analysis of these data and can request additional data if necessary. All data will initially be provided to the DSMB without indication of treatment group allocation.

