Similar to AEs, given the high acuity of diseases and morbidity related to critical illness in the patient population under study (over age 65 years old receiving invasive or non-invasive mechanical ventilation and requiring restraint), it is difficult to identify an SAE within the constellation of symptoms related to the normal evolution of critical illness. Only ‘unexpected’ SAEs (inconsistent with underlying pathophysiology or progression of underlying disease) will be collected and reported. Expected SAEs will not be reported (see description below). The investigator will use his/her judgment in determining whether an event is considered to be reportable per guidelines. SAEs will be documented in the participant medical record and/or study file. It is the responsibility of the investigator to review all documentation (e.g. hospital progress notes, laboratory results, diagnostic reports, etc.) regarding each event. This reporting process is outlined below.

3.A. DEFINITION OF SERIOUS ADVERSE EVENTS (SAEs)

An event will be considered an SAE if it meets any one or more of the following criteria:

- A. Results in death
- B. Is life-threatening - an event where a participant is at risk of death at the time of the event. It does not refer to an event that hypothetically might have caused death if it was more severe.
- C. Prolongation of hospitalization - any substantial extension of an inpatient hospitalization beyond the stay anticipated/required in relation to participant's condition prior to the SAE, as determined by the investigator or treating physician.
- D. Results in Disability or Incapacity - is defined as a substantial disruption of a person's ability to conduct normal life functions.
- E. Led to fetal distress, fetal death or a congenital abnormality or birth defect
- F. Important medical event - are those that may not be immediately life-threatening, but may jeopardize the participant and may require intervention to prevent one of the other serious outcomes listed above.

3.B. EXPECTED SAEs

As the patient population under study are hospitalized and critically ill at baseline, care must be taken to determine if an event is outside of what would be expected given the degree and nature of the critical

illness prior to the serious adverse event. In the population under study, some examples of potential expected SAEs include:

- Abnormalities in oxygenation and/or ventilation expected for the degree of injuries sustained.

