- Fluctuations in hemodynamic measures expected for the degree of injuries sustained.
- Agitation and/or pain responses expected for the degree of injuries sustained.
- Complications directly related to sustained injuries.
- Use of medications, blood products, support devices and other therapies expected for the degree of injuries sustained.

3.c. *Expected Deaths*

Importantly, as approximately 15-25% of participants will die from their critical illness, we anticipate that deaths in this study will be expected and occur as a result of the patients' underlying illness, with associated mortality data recorded in the CRF. Please note that reporting an expected death as an SAE via the electronic database report form is not required. However, it is left to each individual site to determine whether it meets local requirements for reporting to the IRB. Unexpected deaths should be reported as described below.

3.D. UNEXPECTED SAEs

All unexpected SAEs must be reported to the PIs and Project Manager using the appropriate form as outlined below.

3.e. Definition of Unexpected SAE

Any SAE occurring in a subject participating in this Trial where the nature, severity, or frequency of the event is not consistent with the expected natural progression of any underlying disease, disorder, or condition of the subject(s) experiencing the adverse event and the subject's predisposing risk factor profile for the adverse event (e.g. sudden death from MI in a person with ARDS and sepsis without known heart disease).

4. Reporting Period

Participants should be monitored for related AEs (to any degree) and unexpected SAEs from the time of randomization until the day after the on-study period is complete (study day 7 for multi-site RCT as participants will be on study for maximum of 6 days, or 24 hours after removal of restraint device under study, whichever is earlier).

5. Reporting Timelines

Related AEs (to any degree – definitely, probably, possibly, or unlikely) and unexpected SAEs should be reported to the PIs and Project Manager ([name], [name], and [name]) within 24h of knowledge of the occurrence of the event. The site is expected to notify the PIs or Project Manager by phone or email and complete the Related AE and Unexpected SAE report form to submit the initial report, as well as any follow-up reports.

5.a. Initial Report

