After the initial report, the investigator is required to monitor and treat the participant until the event is resolved, stabilizes, or otherwise explained. New or updated information will be recorded until the event information is considered complete.

5.c. Expedited Reporting

Safety events that fulfill the following criteria require specific expedited reporting timelines to the DSMB And NIA: Unexpected SAE and definitely related, probably related, possibly related, or unlikely related to study participation.

Once the site submits the event report to the PIs and Project Manager, the SC will review the report and determine whether it meets the criteria for expedited reporting. If the unexpected SAE is considered definitely related, probably related, possibly related, or unlikely related to study participation, the study leadership will generate an expedited event report that will be submitted to the DSMB and the NIA within 3 working days of receiving the site's report.

5.c. General Event Reporting to the Safety Officer and the DSMB

Any safety event that is an unexpected SAE and related (to any degree) to study participation will be reported to the DSMB and to the Safety Officer in expedited fashion, as described above in 5.c.

Withdrawal Procedures: Define the precise criteria for withdrawing subjects from the study. Include a description of study requirements for when a subject withdraws him or herself from the study (if applicable).

Once patients who did not have decisional capacity at the time of initial consent regain that capacity, they will be re-consented for ongoing participation in the study. A patient's decisional capacity will be determined by his or her treating physician using accepted standards for determining decisional capacity and will be confirmed, in

a similar manner, by the research staff, as part of the informed consent process. For all participants, it will be emphasized that participation is voluntary, that all steps involved with participation are voluntary, and that they are allowed to decline to complete any activity or to answer any question they are asked. For all participants, it will be emphasized that they may withdraw from the study or any study procedures at any time without any loss of rights or benefits to which they are otherwise entitled and without losing status or standing within the institution.

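### The risk section promises the DSMB every SAE possibly related to the restraint, but the reporting rules cover only unexpected SAEs, and all deaths are not assured of reaching the DSMB

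*Combined protocol and SAP*

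**What the plan says.** Two parts of the combined protocol and SAP set the rule for SAEs.

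- **Protections against Risk.** Possible relatedness is the only trigger: "Serious adverse events that might bear any relationship to the intervention will be reported to the local IRB". The recipients also include the parent site's "Human Subjects Committee (parent site) and the DSMB, which may elect to restrict or cease enrollment". The section refers the reader on to the Data and Safety Monitoring Plan.
- **Section 3, SAE Reporting.** Only unexpected SAEs are in scope, meaning those "inconsistent with underlying pathophysiology or progression of underlying disease) will be collected and reported". For the rest: "Expected SAEs will not be reported (see description below".
- **Section 3.B, Expected SAEs.** One listed example is "Agitation and/or pain responses expected for the degree of injuries sustained".
- **Section 3.c, Expected Deaths.** Mortality is put at about 15-25%, and "we anticipate that deaths in this study will be expected and occur as a result of the patients' underlying illness". Mortality data go in the CRF. An SAE form for an expected death is not required, and each site decides whether its IRB must be told.
- **Section 5.a, Assessment of Causality.** The investigator must assess relatedness for unexpected SAEs.
- **Section 5.c, General Event Reporting.** "Any safety event that is an unexpected SAE and related (to any degree) to study participation will be reported to the DSMB". The expedited rule just before it has the same two conditions and counts an unlikely relation as related.
- **Data Safety Monitoring Plan, Interim meetings.** "The DSMB will receive cumulative data, including safety events that are reported to the IRB", together with major clinical outcome variables that are not listed. The DSMB may request more.

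**The concern.** The safeguard described to the IRB and the rule the sites will follow are different. A site that follows sections 3 to 5 exactly will break the promise in the risk section whenever an SAE is classed as expected yet might be due to the restraint. No causality assessment is required for such an event, so nothing in the SAE process would show that the promise had been missed.

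This matters more here than in many ICU trials for three reasons. Expectedness is measured against critical illness, not against known effects of the device. The person judging it knows which device the patient is wearing. And the examples of expected events overlap with plausible restraint effects: agitation is an outcome the device is meant to change (Aim 3, hypothesis b), and upper-extremity joint pain is a device event of interest in section 1 of the reporting plan.

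For deaths the risk is uneven reporting. Whether an expected death enters the DSMB package as an IRB-reported event depends on local IRB policy at each of the three sites. The plan gives safety as the DSMB's main charge.

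**Working it through.** **Step 1: follow one event through the text.** Take an SAE that the investigator classes as expected for the illness but that might be related to the restraint.

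| Section | Treatment of this SAE |
|---|---|
| Protections against Risk | Reported to local IRB, parent-site committee and DSMB |
| 3, SAE Reporting | Not collected, not reported |
| 5.a, Causality | No assessment required |
| 5.c, both paragraphs | Fails the unexpected condition, so not sent to the DSMB |

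The first row and the other three cannot all be followed.

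**Step 2: AEs.** Section 2 limits AE reporting to events that are both unexpected and related. Sections 4 and 5 speak of AEs related to any degree, with no expectedness condition, and send them to the PIs and Project Manager within 24 hours. These also disagree, and the DSMB is not a recipient under either.

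**Step 3: deaths.** Mortality is not an outcome in Table 7 and is not named under Interim meetings. The possible routes to the DSMB are an unexpected-SAE report, a site's decision to tell its IRB, the unlisted outcome variables, the retention data, or a DSMB request. None guarantees a complete count.

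**Step 4: scale.** The plan gives no count of deaths to reproduce. Inputs: mortality 15-25% (section 3.c), total N = 54, interim n = 27 (Interim meetings).

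- Total: 54 × 0.15 = 8.1; 54 × 0.25 = 13.5.
- Interim: 27 × 0.15 = 4.05; 27 × 0.25 = 6.75.

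These are upper figures. The 15-25% has no time horizon. Reporting ends at study day 7, or 24 hours after device removal if earlier. Patients expected to die within 6 days are excluded.

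**Step 5: would a test show an imbalance?** Assume 13 vs 14 patients at the interim and 27 vs 27 at the end, with a two-sided Fisher exact test at 0.05.

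- Interim, 5 deaths: 5-0 is needed (p = 0.016 if all are in the group of 13, 0.041 if all are in the group of 14). With 4 deaths, even 4-0 reaches 0.05 only if all are in the group of 13 (p = 0.041).
- End, 8 deaths: 8-0 is needed (p = 0.004). End, 13 deaths: 11-2 (p = 0.009).
- Exact power for a doubled death rate at the interim, with the group of 14 at the higher rate: 9% (15% to 30%) and 20% (25% to 50%). At the end: 16% and 37%.

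A test would usually miss even a doubling. The DSMB would have to read the individual deaths, which requires a complete list.

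**The case against.** The strongest reply is that the gap is narrow and the DSMB has other routes.

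- **Definitions.** Section 3.e makes an SAE unexpected if its nature, severity or frequency does not fit the natural course of disease. An investigator who blames the restraint is largely saying that. The category of possible relation also requires that other conditions do not reasonably explain the event. Read literally, the overlap is mainly events of unlikely relation. This stands and limits the number of events. It does not remove the conflict, because section 5.c itself counts an unlikely relation as related, and no relatedness judgement is required once an event is called expected.
- **Agitation and pain.** A reader might infer that these are dropped outright. They are not: section 3.B covers only responses expected for the degree of injury. Agitation is also measured by RASS and video, and self-extubation is a secondary outcome. But RASS scores carry no judgement of seriousness or cause, and eligibility rests on ventilation and a restraint order, not on injury, so the qualifier gives sites little to apply.
- **Deaths.** A reader might infer that deaths are hidden from the DSMB, or that it cannot see a group imbalance. The documents do not support this. Mortality is in the CRF, unexpected deaths must be reported, the description of the DSMB data is not exhaustive, group labels are withheld only initially, and the DSMB may request data. It also reviews and approves the plan for transmitting SAEs before the RCT starts. This is a gap in specification, not an exclusion. A request, however, depends on someone suspecting a problem, and expected SAEs other than deaths have no stated SAE data set from which to answer it.

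**Conclusion.** The contradiction is real and rests on the text alone: the risk section's promise cannot be kept under sections 3, 5.a and 5.c for an SAE classed as expected but possibly related. How many such SAEs there would be is unknown, since the rule does not collect them. On deaths the supported conclusion is weaker: the DSMB is not assured of seeing them all. The scale, at most about 8 to 14 overall and 4 to 7 at the interim, assumes that the whole 15-25% falls inside the reporting window, which is unlikely. Because both groups wear both devices on Days 1 and 2, a comparison of deaths by randomised group mainly reflects the Day 3 to 6 allocation. No sample size or efficacy analysis is affected. The documents should be reconciled before enrolment.

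**What to change.** 1. Use one SAE rule in Protections against Risk and in sections 3 to 5. In section 5.a, require a relatedness judgement for every SAE. In sections 3 to 3.e and both 5.c paragraphs, collect every SAE judged related to any degree and send it to the DSMB regardless of expectedness. Keep the unexpected criterion only for SAEs judged not related.
2. In the same edit, reconcile section 2 (AEs unexpected and related) with sections 4 and 5 (AEs related to any degree).
3. Under Interim meetings, name a table of all deaths from the CRF by coded randomised group, with the device worn at death or last worn. The device column is needed because of the crossover on Days 1 and 2.

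A blanket bar on classing any event during restraint wear as expected would be too broad, since it could take in most ICU events while a patient is restrained.

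Cost: wording changes, one table drawn largely from data already in the CRF, and somewhat more SAE assessments and forms for sites.

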- **Study Sites:** We will recruit patients from 3 hospitals: UVM, JHU and UCLA. These sites were selected due to successful prior collaborations, experience in ICU RCT recruitment, similar sedation practice (Prelim Data 6), experience in ICU mobility/actigraphy, and similar “usual care” (Prelim Data 6). A study overview is in Figure 3.

- **Data Coordinating:** Data coordination will occur through integrated efforts between Healthy Design and all 3 study sites, with full support for design, conduct, monitoring, and analysis. An employed data coordinator will create a study database in RedCAP

and will manage data from all 3 enrolling sites. Data coordination, cleaning, and subsequent analyses will be overseen by Drs. [name] (PhD biostatistics faculty/ co-I) with Drs. [name], [name], and [name]. [name] will oversee RCT conduct, including regulatory/ NIH reports. And employed study monitor will conduct site monitoring visits during the RCT.

- **Study Leadership of RCT:** To address leadership and communication issues, an Executive Committee (“EC”: Drs. [name], [name], and [name], along with [name] [Project Manager, UVM]) will meet twice monthly by phone to discuss RCT conduct. For issues that require broader input, the RCT also will have a Steering Committee that includes the EC plus Drs. [name] (UCLA site PI), [name] (Biostatistician), [name] (Nurse co-investigator), [name] (aging/delirium co-investigator) that will meet monthly or as needed. Each site-PI will supervise daily operations, along with site research staff supported by per-patient capitation payments. All investigators will co-author publications, with author order mutually agreed upon in advance.
- **Patients (n=54):** Eligibility criteria are identical to the cohort study in Aim 2 (Table 5).
- **Consent:** As in the study in Aim 2 (STTR Phase I), consent will most often occur via LARs with participant re-consent upon regaining capacity. See below under section on Consent.
- **Randomization:** After consent, patients will be randomized (1:1) to Group A vs B (Fig. 4) via UVM’s web-based system (24 hrs/day), with variable-sized blocks of 2 or 4, stratified by site.

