which time they will be observed by research and nursing personnel, with validated and reliable hourly assessments of sedation/agitation (RASS score). A digital video camera will be set up at the foot of the patient's bed to continuously record his/her movements during the study sessions. Overnight between study Days 1-2 and 2-3, subjects will resume traditional wrist restraints, as per MD order. No sensor or video data will be recorded during overnight periods when study staff are not available. Starting on Day 3 morning, subjects who continue to require restraints (per MD order) will be placed in either traditional or novel restraints device, as per their original randomization (i.e. the device worn for first 4-hr study period on Day 1) for up to 4 more days (i.e. until earliest of restraints no longer needed, death, or ICU discharge). This novel within-patient crossover design allows for increased precision with fewer subjects (see Sample Size) because it controls for confounding effects of patient-specific characteristics via each patient serving as their own control when comparing outcomes (i.e. arm activity) of the novel vs. traditional restraint during Days 1 and 2, along with reduced bias due to randomized allocation of initial study group (novel vs. traditional). Moreover, this design permits more prolonged comparison of novel vs. traditional device (over Days 3 to 6) to measure secondary outcomes (e.g., agitation, delirium, and medication use) that are more accurately evaluated over longer periods of evaluation. The randomization feature of this study design also controls for potential temporal differences in movement (e.g., patient more awake/mobile from 9am-1pm vs. 1pm-5pm). Patient eligibility criteria also help ensure that the study occurs when patients require restraint and are readily assessed for the primary and secondary outcome measures.

- Recurrence of clinical need for restraint and/or ICU readmit:** If a patient ceases to need restraint during the 6-day study period, but then is deemed to need restraint again, the randomly allocated intervention will resume (up to 6-day maximum), with study ending upon ICU discharge (without re-starting if ICU re-admit).

Table 7: Primary & Secondary Outcomes of Efficacy RCT in Aim 3

Outcome		Instrument	Scale	Assessment Timing
Primary Outcome				
1	Upper extremity mobility	Actigraphy (total activity counts per 4 hours)	Continuous	Continuously throughout study
Secondary Outcomes				

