The novel restraint device being tested in the FREEDOM Trial is considered so low-risk that it is exempt

from FDA IDE regulations. Nevertheless, participants will be monitored for medical events of interest including skin laceration, upper extremity joint pain, and equipment damage that may not be serious but may be related to the novel restraint intervention. These data will be collected daily while the subject is on study (through day 3 for the pilot study and day 7 for the RCT). These data will be recorded in the electronic database.

2. *Adverse Event (AE) Reporting*

Given the high acuity of diseases and morbidity related to critical illness in the patient population under study (over age 60 years old receiving invasive or non-invasive mechanical ventilation and requiring restraint), it is difficult to identify an adverse event (AE) within the constellation of symptoms related to the normal evolution of critical illness. Therefore, expected AEs (e.g. abnormal laboratory values, aberrant physiology such as fever or tachycardia or hypotension, etc.) consistent with the underlying pathophysiology or progression of underlying illness will neither be collected nor reported. Only AEs that are both unexpected and felt to be related (to any degree) to the novel restraint device will be collected and reported, the majority of which will be considered “events of interest” as above. The investigator will use his/her judgment to determine whether an AE is considered to be definitely related, probably related, possibly related, unlikely related, or not related (see table below in 5.a.). These unexpected and related (to any degree) AEs will be documented in the participant medical record and/or study file. It is the responsibility of the investigator to review all documentation (e.g. hospital progress notes, laboratory results, diagnostic reports, etc.) regarding each event. This reporting process is outlined below.

3. *Serious Adverse Event (SAE) Reporting*

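### AE and SAE monitoring can stop 24 hours after removal of an undefined study device, so safety follow-up depends on restraint duration or on the group, and resumed restraint may go unmonitored

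*Combined protocol and SAP*

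**What the plan says.** Four parts of the combined protocol and SAP bear on this.

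- **Adverse event plan, 4. Reporting Period.** Related AEs and unexpected SAEs are monitored "from the time of randomization until the day after the on-study period is complete". For the RCT this is study day 7, because "participants will be on study for maximum of 6 days". The sentence then adds an alternative end, "or 24 hours after removal of restraint device under study, whichever is earlier". The device is not identified.
- **Adverse event plan, 1. Events of Interest and 2. AE Reporting.** Skin laceration, upper extremity joint pain and equipment damage are examples of events of interest. The rule for them is: "These data will be collected daily while the subject is on study (through day 3 for the pilot study and day 7 for the RCT"). Device removal is not mentioned. Section 2 limits AE collection to unexpected events related to the novel device, "the majority of which will be considered “events of interest” as above".
- **Implementation of the RCT intervention.** After the Day 1 and Day 2 crossover, each patient who still needs restraint wears the device worn first on Day 1, for up to four more days. If restraint stops and is needed again, "the randomly allocated intervention will resume (up to 6-day maximum"). The study ends at ICU discharge.
- **Statistical Analysis Plan, a) Summary for all Aims.** Activity, agitation, delirium and medication use are measured to ICU discharge, death or Day 6, whether or not a device is on.

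**The concern.** Two stop rules apply to largely the same events, and the one for AEs and SAEs depends on an undefined term. A window that closes with device removal closes at a time fixed after randomisation. The device is intended to reduce agitation and sedation, so it could itself change when restraint, and hence follow-up, ends. If the term means only the novel device, the window depends directly on the allocated group.

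The rule is also silent on resumption. Removal does not take a patient off study, and restraint may restart within the six days. Nothing says that AE and SAE monitoring reopens when it does.

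Safety is the main charge of the data safety monitoring board, which reviews cumulative safety data after 27 patients. Unexpected SAEs are collected in all participants, with causality judged against study participation. For these events, unequal or interrupted observation could mislead.

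**Working it through.** **The plan's own figure.** The RCT has at most 6 days on study, and 6 + 1 = day 7. The pilot has 2 days, and 2 + 1 = day 3. Both agree with the Events of Interest section ("through day 3 for the pilot study and day 7 for the RCT").

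**Inputs.** Allocation is 1:1 ("patients will be randomized (1:1) to Group A vs B"). The periods are 9am-1pm and 1pm-5pm, with device order reversed on Day 2. Exersides therefore last comes off at 1pm on Day 2 in the wrist-first group. In the Exersides-first group it comes off at 5pm on Day 2, or later if restraint is still needed on Days 3-6.

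**Assumptions.** The clock starts at 9am on Day 1 in both groups, Days 3-6 wear ends at midnight on the last day of need, and day 7 means the end of that day. Removal means last removal.

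**Formula.** Window = min(removal + 24 h, end of day 7) − 9am on Day 1. The maximum is 6 × 24 + 24 − 9 = 159 h.

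**If the term means Exersides only.** In the wrist-first group, 1pm on Day 2 plus 24 h is 1pm on Day 3, which is 48 + 4 = 52 h after the start.

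| Restraint need ends | Exersides-first (h) | Wrist-first (h) | Difference (h) | Ratio |
|---|---|---|---|---|
| Day 2 | 56 | 52 | 4 | 1.08 |
| Day 3 | 87 | 52 | 35 | 1.67 |
| Day 4 | 111 | 52 | 59 | 2.13 |
| Day 5 | 135 | 52 | 83 | 2.60 |
| Day 6 | 159 | 52 | 107 | 3.06 |

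The wrist-first group has between 1 − 52/56 = 7% and 1 − 52/159 = 67% less follow-up time. If Day 6 removal is at 9am or 5pm, the Exersides-first window is 144 or 152 h.

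**If the term means either restraint.** Windows are equal for equal restraint need: 63, 87, 111, 135 or 159 h when need ends on Day 2, 3, 4, 5 or 6. Against collection to day 7, this leaves 4, 3, 2, 1 or 0 days uncovered. The groups differ only if their restraint durations differ.

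**Resumption.** Suppose restraint stops at the end of Day 3 and resumes on Day 5, which the six-day maximum allows. Counted from that removal, the AE/SAE window closes at the end of Day 4, and device wear on Days 5 and 6 falls outside it. Counting from the last removal does not help in practice, because staff cannot know which removal is the last.

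**With one fixed end at day 7.** Both groups have the same maximum of 159 h, subject to death or discharge.

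**The case against.** The strongest reply is that the two sections cover different things. The day 7 rule governs events of interest and the removal clause governs reporting of related AEs and unexpected SAEs. Daily collection also applies only while on study, so day 7 may be a maximum. This narrows the conflict but does not remove it. The protocol says most reportable AEs are events of interest, and the intervention and analysis sections keep patients under study after removal.

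A second reply is that either restraint is the more natural meaning. The AE sections say novel device when they mean Exersides, and the Reporting Period sentence is anchored to the on-study period, which continues for both groups on Days 3-6. This stands. The built-in difference between groups is therefore the less natural reading, and what remains is dependence on restraint duration.

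A reader might infer more than the documents support:

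- **That one group would show 57% fewer events** ((7 − 3)/7, counting whole days). This needs the Exersides-only reading, restraint through Day 6 and a constant event rate. A constant rate is implausible for AEs defined as related to a device that the wrist-first group no longer wears after Day 2.
- **That delayed joint pain is lost.** It is a named event of interest and is still collected to day 7. Section 5.b also follows reported events until they resolve, stabilise or are explained, although this does not capture new events.
- **That equal windows would make AE counts comparable between groups.** Related-AE capture is tied to the novel device in any case, and the SAP plans no AE or SAE comparison between groups.

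**Conclusion.** The point holds as an inconsistency that should be corrected. As written, AE and SAE follow-up ends at a time that depends on when restraint stops or, on the less natural reading, on the allocated group. On either reading, a patient restrained again after more than 24 hours could wear a study device outside the stated window.

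The size is a range and not an estimate. Up to four days before day 7 are uncovered if either restraint counts. If only Exersides counts, the windows are 52 h against 56 to 159 h. Both rest on the timing assumptions above and on restraint duration, which the documents do not give. These are differences in observation time, not in expected event counts.

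The consequence is mainly for unexpected SAEs and for related AEs that are not events of interest. The primary endpoint (actigraphy on Days 1 and 2), the sample size of 54 and the power are unaffected.

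**What to change.** Reconcile the Reporting Period, Events of Interest, RCT intervention and Statistical Analysis Plan text to one AE and SAE data-collection window that:

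- does not depend on device removal;
- is the same for all randomised patients (the Events of Interest section already states day 7);
- covers any resumption of restraint; and
- states how it ends at death or ICU discharge, since the intervention section ends the study at ICU discharge.

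If the term device under study is kept anywhere, define it. This concerns data collection only and changes no clinical management.

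The cost is a few sentences of protocol text and a short daily event check for up to four more days in some patients still under study. If the window is to run past ICU discharge, some follow-up outside the ICU would be needed as well, so that choice should be made explicitly.
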